4 STUDY DESIGN

4.1 OVERALL DESIGN

This is an open-label real world study that has been designed to determine the patterns of use and impact of inhalation parameters on both predicting asthma exacerbations and response to biologics in patients with severe asthma. The digital inhalers used in this trial are unique in their ability to seamlessly record multiple parameters as the patients use their inhalers. There are no external devices required for device use recording. We aim to leverage the information collected by the digital inhaler to understand the impact of exacerbations on inhalation parameters, to determine the clinically meaningful differences in these measurements, and to determine their correlation to FEV1, which is the most widely accepted measure of airflow in patients with severe asthma. Home spirometry is challenging and expensive and if inspiratory flow measures can be used as surrogates of expiratory flow, this would revolutionize our ability to track lung function in patients with severe asthma. The digital parameters will be incorporated with clinical, digital, and biological markers in an attempt to identify predictive algorithms that can identify responders to biologics early in the treatment course, facilitating decisions about continuation or discontinuation of therapy.

4.2 SCIENTIFIC RATIONALE FOR STUDY DESIGN

We designed an open label, single site study and intend to enroll patients in a sequential manner via screening of the EMR system for patients currently receiving biologics or with a pending approval for biologics for asthma. The open label design was selected as we are interested predominantly in inhalation parameters that are collected without any specific actions from participants, thus decreasing any potential changes in medication utilization. We intend to educate the patients on the use of the inhaler and how it has been prescribed but will make no efforts to intervene to encourage compliance with medication utilization, as we are interested in patient behavior and interaction with the device. The application that collects information about inhaler use will be stored on the patients' smart phone, and therefore they may choose to review the information and make changes in their adherence. We will not require patients to utilize the application and will passively record whether patients report using the app or not. We will design a questionnaire that determines patients' opinions of the app if they are utilizing it. All clinical parameters will be collected from the EMR.

Our main objective is to determine baseline inhalation parameters (e.g., peak inspiratory flow) using sample means. According to one study (<https://www.ncbi.nlm.nih.gov/pmc/articles/PMC5328129/>) the PIF mean was 115 and standard deviation was 15. Assuming a 100 patient sample, the 95% CI of our estimate of the PIF sample mean would be plus or minus 3, e.g., 115 (95% CI 112 – 118), which we deem to be of sufficient power for our analysis (<http://statulator.com/SampleSize/ss1M.html>).

Our secondary objective includes training a machine learning model, and one common measure to evaluate model performance is discrimination, assessed by an area under the ROC curve (AUROC). Again, assuming a 100 patient sample and a 50% event rate, we would have adequate power to conclude that a model with an AUROC performance of >0.65 has confidence intervals that won't cross 0.5 (which would be a model that is no better than chance) (<http://www.biosoft.hacettepe.edu.tr/easyROC/>).

4.3 JUSTIFICATION FOR DOSE

We intend to use the approved dosage of the IMP. No changes to therapy were warranted in this study.

4.4 END OF STUDY DEFINITION

There are no formal rules for early termination of this study. During the conduct of the study, serious adverse events will be reviewed as they are reported from the study site to identify safety concerns.

The study may be terminated by the sponsor for any reason at any time. For example, the sponsor should terminate the study in the event of the following:

- new toxicological or pharmacological findings or safety issues invalidate the earlier positive benefit-risk assessment
- discontinuation of the development of the IMP or device

If the whole study is stopped, patients who are terminated early will be followed according to withdrawal criteria and procedures for the patient.

5 STUDY POPULATION

5.1 INCLUSION CRITERIA

1. A history of severe persistent asthma as defined by ERS/ATS criteria which includes the presence of poor asthma control on high dose ICS/LABA OR the need for high dose ICS/LABA to maintain asthma control OR oral steroids for maintenance therapy for more than 50% of the prior year.
2. Age >18 years of age or older.
3. Presence of current biologic use or planned initiation of biologics following study enrollment.
4. Patients will be categorized on the basis of asthma control (ACT < 19 will be considered poor asthma control). We will cap the patients with good asthma control at 30% and will no longer enroll those patients once the strata have been fully enrolled.
5. Willingness to switch maintenance inhalers to AirDuo® Digihaler™ and/or to use ProAir® Digihaler™ for rescue therapy. Use of nebulized albuterol will be discouraged but not prohibited. We will require patients to document nebulizer use. Patients that discontinue Pro-Air will be asked to document use of their rescue inhalers in their diaries.
6. Can read and communicate in English and is familiar with and is willing to use his/her own smart device and download and use the study application. If their smart device is not compatible with the study software; willingness to use an alternative device that will be provided by the study team.
7. Ability to provide informed consent.
8. The patient must be willing and able to comply with study requirements and restrictions and to remain at the investigational center for the required duration during the study period, and willing to return to the investigational center for the follow-up procedures and assessments as specified in this protocol.

5.2 EXCLUSION CRITERIA

1. Clinically important pulmonary disease including COPD, primary bronchiectasis, idiopathic pulmonary fibrosis, cystic fibrosis and interstitial lung disease.
2. Any disorder that is either not stable or could in the opinion of the investigator affect the ability of the subject to safely participate in the study or could adversely affect study results.
3. History of HIV or other primary immunodeficiency syndrome.

4. Malignancy other than skin cancer that has occurred within the past year and that will impact survival thus limit participation in the clinical trial.
5. Current documented alcohol abuse or drug use. Patients with a history of abuse and are in remission are eligible to enroll.
6. Any life-threatening diseases that will impact the patient's ability to complete the 12-month study period.
7. Inability to provide informed consent.

5.3 LIFESTYLE CONSIDERATIONS

There are no lifestyle considerations for this study.

5.4 SCREEN FAILURES

Patients will - be removed from the study if they do not get started on a biologic or if they discontinue therapy with biologics for any reason.

Patients who screen fail do not need to be replaced to reach the target enrollment number.

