5. To evaluate the asthma control and health care utilization of subjects as measured by the number of exacerbations (acute worsening of asthma requiring at least 3 days of corticosteroids or a doubling dose of maintenance steroids), Emergency and hospitalization encounters, and patient-reported perceptions of asthma control.
6. To employ machine learning techniques to a robust well characterized cohort with clinical, biological, and digital markers to develop a predictive algorithm aimed at identifying responders to biologics. In addition, we would aim to develop an algorithm that can detect early changes in measured parameters that can predict long-term improvements in asthma control and exacerbations when biologics are initiated. The latter objective will be achieved by focusing on the subgroup of patients initiating biologics for the first time or switching between biologics due to perceived inadequate response.

Endpoints:

Primary Endpoint:

Mean and median number of (daily) doses of ProAir® Digihaler™ and AirDuo® Digihaler™ utilized at baseline, temporal patterns in rescue and controller medication utilization, and within-patient parameter mean, median, and variance per-inhalation to establish baselines.

Secondary Endpoints:

1. Proportion of patients with different rates of adherence.
2. Proportion of Patients achieving non-response, partial-responses, and complete response to biologics.
3. Change in Main Peak Inspiratory volume from baseline up to one year.
4. Change in Mean Inspiratory Time from baseline up to one year.
5. Change in mean peak inspiratory flow (PIF) from baseline up to one year.
6. Change in mean forced expiratory volume in one second (FEV1) from baseline up to one year.

Exploratory Endpoints

7. Number of exacerbations from baseline up to one year.
8. Number of hospitalizations.

9. Number of emergency room visits.
10. Mean Asthma Control Test (ACT) scores.
11. Algorithm that produces a daily asthma exacerbation probability given a set of baseline and current inhalation parameters. A confusion matrix summarizing the algorithm's performance on training dataset and from which performance statistics (accuracy, sensitivity, specificity, etc.) can be computed.

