7.2 PARTICIPANT DISCONTINUATION/WITHDRAWAL FROM THE STUDY

1. Patient withdraws consent or withdrawal from the study for any reason
2. Patient experiences an adverse event or other medical condition which indicates to the investigator that continued participation is not in the best interest of the patient.
3. Patient develops an illness that would interfere with his/her continued participation.
4. Patient is noncompliant with the study procedures and assessments in the opinion of the investigator.

Patients should be treated with standard of care after withdrawal from or termination of the study as appropriate. We will obtain information on patients in the case of withdrawal from the study or discontinuation from IMP. Results of any evaluations and observations, together with a narrative describing the reason(s) for withdrawal from the study or discontinuation from IMP, must be recorded in the source documents. The case report form (CRF) must document the primary reason for withdrawal from the study or discontinuation from IMP.

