8.3.4 SERIOUS ADVERSE EVENT REPORTING

In keeping with good clinical practice or good pharmacovigilance practice, and 21 C.F.R. Part 314 as the case may be, the external sponsor/collaborator will be required to report and notify the FDA, Institutional Review Boards (IRBs), Teva Pharmaceuticals (Teva), and any other collaborators/investigators of all situations mentioned below, within twenty-four (24) hours from receiving information of the situation. The event will be reported to Teva by submitting the collected information to the Teva Local Safety Officer.

- (a) All related Serious Adverse Events
- (b) All Serious Adverse Device Effects
- (c) Any medical event which may reasonably be believed to impair the integrity, validity or ongoing viability of the Study

Adverse Event. Sponsor/collaborator acknowledges that Company is required to comply fully and promptly with all regulatory safety reporting requirements regarding its products. The investigator being the sponsor of the study has sole responsibility for reporting of adverse events to the FDA, IRBs and/or investigators. For informational purposes any correspondence to the FDA regarding adverse events or other safety issues will be simultaneously copied to the Company via email ([contact]) or [contact]). The Investigator will communicate the occurrence of any serious adverse events which he or she believes to be definitely, likely, possibly or probably related to the Study Product, and any exposure of a pregnant study participant to the Study Product, within 24 hours of becoming aware of the event. In the case of non-interventional studies, the Investigator also will communicate all related, non-serious adverse events to Company within 24 hours of becoming aware of the event. Please note that the reporting period begins when a patient signs the informed consent, and ends 30 days after the discontinuation of dosing or completion of the patient's participation in the Study if the last scheduled visit occurs at a later time. In addition, the Investigator must notify Company of any serious adverse events that may occur after this time period which he or she believes to be definitely, likely, possibly or probably related to the Study Product.

The MedWatch 3500A form should be utilized to report serious adverse events to the FDA.

A serious adverse event or reaction is any untoward medical occurrence that at any dose:

- Results in death;

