9.3 POPULATIONS FOR ANALYSES

University of Michigan patients currently receiving biologics or with a pending approval for biologics for asthma.

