3. Patients will be assigned to one of three adherence groups (low, moderate, high) based on Digihaler™ inhalation usage parameters over the previous month. We will use the Chi-squared test to determine if group differences exist for each asthma outcome over the next month, and Tukey's Honest Significant Difference test to determine which groups are significantly different.

4. Patients will be assigned to one of three biologics response groups (non, partial, complete) based on six asthma factors (described earlier). We will use the Chi-squared test to determine if group differences exist for each inhalation parameter, and Tukey's Honest Significant Difference test to determine which groups are significantly different.

5. To develop an algorithm that can predict patients that will respond to biologics regression or classification models. Since we expect our training set to be relatively small with a low event rate, we plan to use the entire inhalation parameter dataset for model training but will employ repeated k-fold cross-validation to reduce variance (over-fitting) and include non-linear features to reduce bias (under-fitting). We do not know a priori whether regression or classification would be the appropriate approach to this question so we will test models using both approaches. The classification approach can be formulated as either a two-class problem – Non vs. Partial or Complete responders, or Non or Partial vs. Complete responders – or a three-class problem – Non vs. Partial vs. Complete. The regression approach requires a two-class formulation using logistic regression. Different models will be fit for different formulations and the performance of each model assessed and compared to others.

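### Section 5.4 removes enrolled patients who stop biologics, and nothing keeps them in the response analyses; if poor responders stop more often, non-response is understated

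*Combined protocol and SAP*

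**What the plan says.** Section 5.4, although headed as a section on screen failures, states that patients are to "be removed from the study if they do not get started on a biologic or if they discontinue therapy with biologics for any reason". Current biologic use is one route to eligibility (section 5.1), so the rule covers people who have been enrolled, given inhalers and followed.

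Response to biologics is used in three places:

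- Secondary endpoint 2 in the synopsis: "Proportion of Patients achieving non-response, partial-responses, and complete response to biologics".
- Section 9.4.3 item 4, as the grouping factor: "Patients will be assigned to one of three biologics response groups (non, partial, complete) based on six asthma factors (described earlier").
- Section 9.4.3 item 5, as the target of the prediction models, with two-class splits "Non vs. Partial or Complete responders, or Non or Partial vs. Complete responders" and a three-class version.

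The analysis population in section 9.3 is one sentence: "University of Michigan patients currently receiving biologics or with a pending approval for biologics for asthma". It does not mention patients removed later.

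Some provision exists after withdrawal. Section 7.2 does not name biologic discontinuation, but its first item is a catch-all that could cover it: "Patient withdraws consent or withdrawal from the study for any reason". The same section says "We will obtain information on patients in the case of withdrawal from the study or discontinuation from IMP" and asks for a narrative and a primary reason on the CRF. In section 8.3.4, "the reporting period begins when a patient signs the informed consent, and ends 30 days after the discontinuation of dosing"; that is a safety-reporting window tied to the study product.

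**The concern.** Stopping a biologic is a natural consequence of not responding to it. A rule that removes patients when they stop therefore ties loss of data to the outcome being classified. No section requires the response factors (exacerbations, maintenance OCS dose, FEV1, ACT, global perception) to be collected after removal. Neither 9.3 nor 9.4.3 says whether a removed patient is classified on earlier data or counted in the denominator.

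If removed patients drop out and are mostly poor responders, the plan reports too little non-response and too much complete response, and the prediction model is trained with its smallest class depleted. Section 4.1 says that the algorithms are meant to inform decisions on continuing or discontinuing therapy, and the patients lost are those for whom that decision went one way.

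Section 5.4 also does not say whether a switch to another biologic counts as discontinuation. The synopsis and section 3 plan a subgroup that includes patients who switch for inadequate response; if a switch counts, the rule removes part of that subgroup.

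**Working it through.** **The plan's own figures.** Section 9.2 gives a half-width of 3 for mean PIF: 1.96 × 15/√100 = 2.94, which agrees. It also says that 100 patients with a 50% event rate keep the interval for an AUROC above 0.65 clear of 0.5. With the Hanley–McNeil standard error at AUROC 0.65 and 50 v 50, SE = 0.0548 and the 95% CI is 0.543–0.757, which agrees.

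**Inputs.** Section 2.1 gives a response mix of 10–15% non-response and 40% complete response, with the remainder (45–50%) partial. It describes patients selected as likely responders and may not fit patients already established on a biologic. No discontinuation rate is given, so every removal fraction below is an assumption.

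**Bounds, with no assumption about who stops.** If a share d of starters is removed unclassified and the reported share among those kept is p, the share among all starters lies between p(1 − d) and p(1 − d) + d. With p = 10%:

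| d | Lower | Upper |
|---|---|---|
| 5% | 9.5% | 14.5% |
| 10% | 9.0% | 19.0% |
| 20% | 8.0% | 28.0% |

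**Illustrations, per 100 starters.** Reported share = true share × (1 − fraction removed), divided by the total kept.

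| Assumed removal | True non-response 10% | True non-response 15% |
|---|---|---|
| 10% of non-responders only | 9/99 = 9.1% | 13.5/98.5 = 13.7% |
| 20% of non-responders only | 8/98 = 8.2% | 12/97 = 12.4% |
| 50% of non-responders only | 5/95 = 5.3% | 7.5/92.5 = 8.1% |
| 20% of every class | 8/80 = 10% | 12/80 = 15% |
| 50% of complete responders only | 10/80 = 12.5% | 15/80 = 18.8% |

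When half of the non-responders are removed, complete response rises from 40% to 40/95 = 42.1% or 40/92.5 = 43.2%. The last two rows show that the direction depends on who stops.

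**Precision of the models.** Half-width = 1.96 × Hanley–McNeil SE at AUROC 0.65, over both mixes and both assignments of the positive class. Fractional counts are expected values.

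| Split | No removal | 10% of non-responders removed | 50% of non-responders removed |
|---|---|---|---|
| Non v partial-or-complete | 0.14–0.19 | 0.15–0.20 | 0.19–0.27 |
| Non-or-partial v complete | 0.11 | – | 0.11 |

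An interval centred on 0.65 reaches 0.5 once the half-width is 0.15. For the first split, 10 v 90 already has a lower limit of 0.46–0.49 with nobody removed. That weakness comes from class imbalance against the assumed 50% event rate; removal adds to it, by an amount that depends on the removal rate.

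**The case against.** The strongest case on the other side has five parts.

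1. *Poor responders are switched, not stopped.* Section 2.1 says that partial and non-responders are moved between biologics, and the planned switcher subgroup suggests that they stay in the study. This stands. It narrows the affected group to patients who stop all biologics. What remains is the same section's mention of discontinuation alongside switching as an outcome of long trials of therapy. That makes differential stopping plausible but gives no frequency. Removal of half of the non-responders should be read as an extreme, not an expectation.

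2. *The data may exist anyway.* Section 8.1.2.1 abstracts clinical data from the EMR into a registry under separate consent, section 5.5 asks providers in other clinics to document response, and section 2.1 places assessment of response at 4–6 months after a new therapy starts. Many who stop could therefore be classified from data before the stop. This is a good reason why the repair is cheap, but no text says that it will be done.

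3. *Section 9.3 can be read as entry status, covering everyone enrolled.* That reading is possible, but the sentence does not address patients whom 5.4 has removed.

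4. *Nobody can be classified yet.* The response rule announces six factors, lists five and gives no cut between partial and complete. That is true. It is a separate defect that must also be repaired, and doing so would not settle who is counted.

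5. *The consequence is limited.* Section 8.1 says that drug efficacy is not evaluated, and the primary endpoint does not use response class. Both stand, and they keep this a modest point.

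A reader might infer more: that data already collected are deleted, that there is no follow-up after withdrawal, or that non-response is certain to be understated. The documents do not support these readings. Nothing says that data are discarded, 7.2 requires some information and a reason, and the bias requires both exclusion from the denominator and unequal stopping.

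**Conclusion.** The concern holds in a conditional form. Section 5.4 is an actual rule that ties leaving the study to the treatment whose response is being classified, and nothing in 7.2, 9.3 or 9.4.3 keeps the removed starters in the response analyses.

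If they leave the denominator and poor responders stop all biologics more often, non-response is understated: slightly under mild removal (true 10–15% reported as about 8.2–13.7% when 10–20% of non-responders are lost), and by about half under the extreme case (5.3–8.1%). Without an assumption about who stops, losing 10% of starters unclassified leaves a reported 10% compatible with 9–19%. The calculations rest on assumed removal fractions, and the illustrations also on the section 2.1 response mix.

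No general loss of precision can be claimed. It is confined in practice to the non v partial-or-complete split and depends on the removal rate. Patients who never start a biologic are not at issue. This is an inexpensive improvement to a secondary analysis and does not threaten the primary result.

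**What to change.** 1. Reconcile 5.4 with 7.2 and with the planned switcher subgroup, and state whether a switch between biologics counts as discontinuation.
2. For patients who started a biologic, replace removal from the study with continued data collection, with consent, from the EMR and MiAsthma Registry and the contacts already scheduled. The monthly calls already cover medications, exacerbations and healthcare use (section 8.1.1.3). Keep data after a stop out of the primary summaries, whose objective concerns patients being treated with biologics.
3. State in 9.3 and 9.4.3 that all starters stay in the response analyses, with one class per patient, based on a single named index biologic course and data up to the stop or switch. One class per patient is needed because the endpoint is a proportion of patients.
4. Add a sensitivity analysis that counts stops of all biologics for inadequate response, and stops that cannot be classified, as non-response. Report switches separately, since partial responders are switched too. Tabulate stops and switches by reason.

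Step 3 also needs a complete response rule, which is a separate point.

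Cost: a protocol amendment with IRB approval and consent-form revision, and modest extra follow-up for a few patients. ACT is scheduled only at clinic visits, and inhalers are returned at early termination, so ACT or Digihaler data may be missing after a stop. No treatment or inhaler-supply rule is proposed.
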